9.3 Recording and reporting of SAEs, SARs AND SUSARs

All **SAEs** occurring from the time of start of trial treatment until 14 days post cessation of trial treatment must be recorded on the Trial data collection form and scanned and emailed to the Sponsor **within 24 hours** of the research staff becoming aware of the event. The original form will be copied and held by the Sponsor.

The Chief Investigator is responsible for ensuring that the assessment of all SAEs for relatedness and expectedness is completed and the onward notification of all SARs to the Sponsor immediately or not more than 24 hours of first notification. The sponsor has to keep detailed records of all SARs reported to them by the trial team.

All SAEs/SARs may be reported by the trial team to Pharmacare UK.

Adverse Reactions will be reported to the REC if they could:

- adversely affect the health of participants
- impact on the conduct of the trial
- alter the risk to benefit ratio of the trial
- alter the competent authority's authorisation to continue the trial in accordance with Directive 2001/20/EC

For each **SAEs** the following information will be collected:

- full details in medical terms and case description
- event duration (start and end dates, if applicable)
- action taken
- outcome
- seriousness criteria
- causality (i.e. relatedness to trial drug / investigation), in the opinion of the investigator
- whether the event would be considered anticipated.

Events will be followed up until the event has resolved or a final outcome has been reached."

BERRY Protocol v 6.2 22.07.2021 IRAS 282732

All SAEs assigned by the PI or delegate (or following central review) as both suspected to be related to treatment and unexpected will be classified as SUSARs and will be subject to expedited reporting to the REC. The sponsor will inform the REC and Manufacturer of SUSARs within the required expedited reporting timescales.”

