Follow up telephone call within 5 days of a positive swab; Verbal Consent and Baseline data collection	Opportunity to raise and discuss any questions about the trial or PIS ^(a) . Eligibility criteria will be checked and electronic or verbal consent will be received. An eligible patient can decline to participate without having to give any reason. After consent, the research team will collect baseline demographics, VAS score, patient symptoms. ^(a)
Ineligible patients	If anyone does not meet the eligibility criteria the research team will explain why and ensure that they have time to ask any questions.
Randomisation and collection of trial treatment	Patients will be randomised to active or placebo liquid and a 14 day supply of study liquid dispensed to take home and start straight away. This can either be collected by a family member or friend and dropped to the patient's doorstep – or the research team will drop to the doorstep so that everyone has a chance to take part. If a participant lives further away the liquid will be delivered to their home address by courier.
Follow Up visits on day 3, 7, 10, 14 and 28	All follow up visits will occur either by phone, text or email depending on participant preference at day to collect the following data: 
 • Current symptoms

BERRY Protocol v 6.2 22.07.2021 IRAS 282732

	
 • How well are you feeling VAS score 0 -100 (0 will be recorded in the case of death) • What are your current symptoms? • Have you started any new medications? • Have you missed any doses of your study liquid? • Experienced any adverse events? • At day 14 – if a participant verbally consented initially, they will be asked to sign a paper consent form which was sent out with their trial liquid and return it in the research team for filing. At day 14 they will also be reminded that they need to stop taking their study liquid.
Notes	(a) This limits the exposure of the research team to the virus during later collection of written consent

BERRY Protocol v 6.2 22.07.2021 IRAS 282732

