7.8 Long term follow-up assessments

With the exception of any pregnancy outcomes, Data collection will end at day 28 following randomisation. Research team will follow up the outcomes of any notified pregnancies.

This will be to check to see if patients have been admitted to hospital in the 28 days following a positive SARS-CoV2 test.

If admitted:

- Date of hospitalisation
- Admission hospital and location (i.e. HDU/ITU) – reason and outcome. Date discharge / death

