9.2 Operational definitions for (S)AEs

BERRY Protocol v 6.2 22.07.2021 IRAS 282732

The following adverse events are known manifestations of COVID-19 related disease. They will not be recorded in the medical notes as (S)AEs as part of this COVID-19 intervention trial.

- Chills
- Loss of taste and/or smell
- Cough
- Bloody sputum
- Sore throat
- Nasal symptoms: blocked or runny nose
- Ear pain
- Wheezing
- Chest tightness
- Shortness of breath
- Muscle aches
- Joint pain /heaviness
- Fatigue
- Headache
- Confusion
- Loss of appetite
- Abdominal pain
- Nausea/vomiting
- Diarrhoea
- Sore, red, gritty eyes
- Skin rash / irritation
- Dry/Sore lips
- Mouth Ulcers
- High Temperature

Evaluation of adverse events

The Sponsor expects that adverse events (apart from expected AEs) are recorded in the medical notes from the point of Informed Consent regardless of whether a participant has yet received a medicinal product. Individual adverse events should be evaluated by the investigator. This includes the evaluation of its seriousness, and any relationship between the investigational medicinal product(s) and/or concomitant therapy and the adverse event (causality).

Assessment of seriousness

Seriousness is assessed against the criteria in section 9.1. This defines whether the event is an adverse event, serious adverse event or a serious adverse reaction

Assessment of causality

Definitely: A causal relationship is clinically/biologically certain. **This is therefore an Adverse Reaction**

Probable: A causal relationship is clinically / biologically highly plausible and there is a plausible time sequence between onset of the AE and administration of the investigational medicinal product and there is a reasonable response on withdrawal. **This is therefore an Adverse Reaction.**

Possible: A causal relationship is clinically / biologically plausible and there is a plausible time sequence between onset of the AE and administration of the investigational medicinal product. **This is therefore an Adverse Reaction.**

BERRY Protocol v 6.2 22.07.2021 IRAS 282732

Unlikely: A causal relation is improbable and another documented cause of the AE is most plausible. **This is therefore an Adverse Event.**

Unrelated: A causal relationship can be definitely excluded and another documented cause of the AE is most plausible. **This is therefore an Adverse Event.**

Unlikely and Unrelated causalities are considered NOT to be trial drug related

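### Section 9.3 ties the SAE reporting window to dosing, which conflicts with the consent start in 9.2, the unlimited duty in 9.4 and the day-28 follow-up

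*Combined protocol and SAP*

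**What the plan says.** Section 9.3 sets the period for SAEs in these words: "occurring from the time of start of trial treatment until 14 days post cessation of trial treatment must be recorded". Its duty has two parts, entry on the trial's own form and an email to the sponsor within 24 hours.

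Other sections use different clocks:

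- **Section 9.2.** Adverse events, apart from the listed COVID-19 manifestations, "are recorded in the medical notes from the point of Informed Consent regardless of whether a participant has yet received a medicinal product". The investigator assesses each for seriousness and causality.
- **Section 9.4.** The principal investigator must see that all SAEs reach the sponsor within 24 hours. No start or end is given. Section 9.9 sets no time limit for SUSARs.
- **Section 7, procedures table.** The contacts are "Follow Up visits on day 3, 7, 10, 14 and 28", and one of the questions is "Experienced any adverse events". The schedule in 7.7 marks adverse events at each contact (±1 day) and at early exit. No contact depends on still taking the liquid.
- **Section 7.8.** "Data collection will end at day 28 following randomisation", with an exception for pregnancy outcomes.

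On treatment, the procedures table provides for "a 14 day supply of study liquid dispensed to take home and start straight away", and adds: "If a participant lives further away the liquid will be delivered to their home address by courier". Section 8.7 mentions stopping treatment and leaving the trial together. Section 7.10 ends data collection when consent is withdrawn. Section 10.7 analyses safety by randomised arm, whether or not the allocated treatment was received.

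**The concern.** The 9.3 window opens and closes with each participant's dosing, while follow-up and the safety analysis are organised by randomisation. Someone who stops the liquid early, for instance after feeling unwell (8.7), has a shorter period of mandatory SAE reporting than someone who completes the course. If early stopping differs between arms, SAEs are sought under the strictest rule for unequal times, and the arm with more early stopping could show fewer of them for that reason alone.

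The sections also disagree on whether a given SAE must be reported at all. An SAE before the first dose, or late in follow-up after an early stop, is outside 9.3 but inside 9.4, and the protocol does not say which governs. Investigators and the research delivery team are unblinded (7.4), so people who know the allocation may be resolving the ambiguity.

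**Working it through.** **Inputs.** Planned treatment is 14 days (trial summary; section 7). The post-cessation period is 14 days (9.3). Data collection ends on day 28 (7.8). Day 1 is the day of randomisation and dispensing (7.7). I read cessation in 9.3 as the participant's own last dose, which is the natural reading but not spelled out.

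**The plan's own figure.** Day-1 start, full course: last dose on day 14, window end 14 + 14 = day 28. This matches 7.8.

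**Early stop, day-1 start.** Window end = last-dose day + 14. Shortfall = 28 − window end.

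| Last dose (day) | 9.3 window ends (day) | Days short of day 28 | Share of 28 days |
|---|---|---|---|
| 1 | 1 + 14 = 15 | 13 | 13/28 = 46% |
| 3 | 3 + 14 = 17 | 11 | 11/28 = 39% |
| 7 | 7 + 14 = 21 | 7 | 7/28 = 25% |
| 10 | 10 + 14 = 24 | 4 | 4/28 = 14% |
| 14 | 14 + 14 = 28 | 0 | 0% |

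**Late start.** The delivery delay is not stated. Assume a first dose d days late with k days taken, so the window ends on day d + k + 14.

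- Full course (k = 14), d = 1, 2, 3: the window ends on day 29, 30, 31, after data collection has closed. The last contact falls between day 27 and day 29.
- d = 3, k = 11: 3 + 11 + 14 = day 28. A late start can offset an early stop.
- No dose taken: the 9.3 window never opens, yet 10.7 keeps the participant in the safety analysis.

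**The same event under each section.**

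| SAE | 9.2 (medical notes) | 9.3 (form, 24 hours) | 9.4 (all SAEs) | Scheduled question |
|---|---|---|---|---|
| After consent, before first dose | yes | no | yes | at next contact |
| More than 14 days after an early stop, before day 28 | yes | no | yes | day 28 |
| After day 28, late starter with full course | no end stated | yes | yes | none; 7.8 has closed |

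**Possible imbalance between arms.** The documents give no rate of early stopping. For illustration only, borrow the 15% dropout allowance in 10.1 as the share of one arm that stops early but stays in the trial, with none in the other. Mean 9.3 coverage would then differ by 0.15 × 4 = 0.6 days (0.6/28 = 2%) if all stopped on day 10, and by 0.15 × 13 = 1.95 days (1.95/28 = 7%) if all stopped on day 1.

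**After the fix.** With a window from consent to at least day 28 for everyone still in the trial, the shortfall is 0 for every last-dose day and the pre-dose gap is 0.

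**The case against.** A reader might infer that anyone who stops early leaves SAE surveillance before day 28. The documents do not support that. A participant who stops the liquid and stays in the trial is still asked about adverse events through day 28, 9.2 requires seriousness to be assessed, 9.4 has no cut-off, and 9.9 sets no limit for SUSARs. Only the explicit 9.3 duty lapses. Nor does it lapse before day 28 for every early stopper, as the late-start example shows.

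A reader might also infer that pre-dose SAEs are lost. They are outside 9.3, but 9.2 puts them in the medical notes and 9.4 has no start point. They cannot be caused by the liquid.

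Much of what matters is captured elsewhere. Section 7.8 checks hospital admissions, with dates, reason and outcome, whatever the dosing, and 9.2 keeps admissions for COVID-19 progression out of SAE reporting altogether. What is exposed is mainly other SAEs late in follow-up among early stoppers who remain in the trial. One qualification: 7.8 counts its 28 days for admissions from the positive test, which may be up to 5 days old at entry (6.1), whereas the table in 3.7 counts from enrolment.

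For a participant who withdraws consent, 7.10 ends collection and rewording 9.3 recovers nothing. Finally, the schedule names no first- or last-dose date, but the CRF is not in the documents and compliance is asked about, so it cannot be said that the dates go uncollected.

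All of this stands, and it limits the size of the problem. It does not remove the conflict: that 9.2 or 9.4 may catch what 9.3 omits shows that the sections disagree.

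**Conclusion.** Sections 9.2, 9.3 and 9.4 and the day-28 follow-up do not give one SAE window. For a day-1 starter who stops the liquid early and stays in the trial, the mandatory form and 24-hour duty in 9.3 ends 13, 11 or 7 days before day 28 for a last dose on day 1, 3 or 7. These are calendar days under one clause. They are not lost SAEs or lost observation.

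It would go too far to conclude that one arm will look safer than it is. That requires early stopping to differ by arm and relevant SAEs to be missed by the other routes, and the documents give no figure for either. The effect on the comparison is unknown and probably small. The sample size of 204, the power and the primary analysis are unaffected.

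The result rests on reading cessation as the participant's own last dose and on counting day 28 on the same scale as day 1. If 7.8 means 28 days after day 1, that is day 29 on this scale and each shortfall grows by one day. The change is still worth making, because it removes a contradiction in safety reporting at almost no cost.

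**What to change.** 1. State one SAE window in 9.2, 9.3 and 9.4: from informed consent to day 28 after randomisation for every participant who has not withdrawn consent, whether or not the liquid is still being taken. Extend it to 14 days after last dose where that is later.
2. Align 7.8 so that SAE data may be collected after day 28 for late starters, and so that the admissions check and the table in 3.7 use the same starting point.
3. Record first-dose and last-dose dates at the existing contacts.
4. Compare SAEs between arms over the common period, randomisation to day 28.
5. Leave the day-28 contact window as it is. Moving it would shift the day-28 VAS, a secondary endpoint, and a few extra days could not be guaranteed to cover a delivery delay of unstated length. SAEs after that contact would come to notice through unscheduled reports, which is another reason to end the comparison at day 28.
6. Reconcile 8.7 and 7.10 so that stopping the liquid is distinguished from withdrawing consent to follow-up.

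The cost is protocol wording, two CRF dates and a few more SAE forms. The contacts and the adverse-event question already exist.

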9.4 Responsibilities

Principal Investigator (PI):

Checking for AEs and ARs when participants attend for treatment / follow-up.

1. Using medical judgement in assigning seriousness, causality and whether the event/reaction was anticipated using the Reference Safety Information approved for the trial.
2. Using medical judgement in assigning seriousness and causality and providing an opinion on whether the event/reaction was anticipated using the Reference Safety Information approved for the trial.
3. Ensuring that all SAEs are recorded and reported to the sponsor within 24 hours of becoming aware of the event and provide further follow-up information as soon as available. Ensuring that SAEs are chased with Sponsor if a record of receipt is not received within 2 working days of initial reporting.
4. Ensuring that AEs and ARs are recorded and reported to the sponsor in line with the requirements of the protocol.

Chief Investigator (CI) / delegate or independent clinical reviewer:

1. Clinical oversight of the safety of patients participating in the trial, including an ongoing review of the risk / benefit.
2. Using medical judgement in assigning the SAEs seriousness, causality and whether the event was anticipated (in line with the Reference Safety Information) where it has not been possible to obtain local medical assessment.
3. Using medical judgement in assigning whether and event/reaction was anticipated or expectedness in line with the Reference Safety Information [in Phase I and early Phase II CTIMPs].
4. Immediate review of all SUSARs.
5. Review of specific SAEs and SARs in accordance with the trial risk assessment and protocol as detailed in the Trial Monitoring Plan.
6. Assigning Medical Dictionary for Regulatory Activities (MedDRA) or Body System coding to all SAEs and SARs.
7. Preparing the clinical sections and final sign off of the Development Safety Update Report (DSUR).

Sponsor: (NB where relevant these can be delegated to CI)

1. Central data collection and verification of AEs, ARs, SAEs, SARs and SUSARs according to the trial protocol onto a database.
2. Reporting safety information to the CI, delegate or independent clinical reviewer for the ongoing assessment of the risk / benefit according to the Trial Monitoring Plan.
3. Reporting safety information to the independent oversight committee identified for the trial Steering Committee (TSC)) according to the Trial Monitoring Plan.
4. Expedited reporting of SUSARs to the REC within required timelines.
5. Notifying Investigators of SUSARs that occur within the trial.
6. The unblinding of a participant for the purpose of expedited SUSAR reporting [For double blind trials only].
7. Checking for (annually) and notifying PIs of updates to the Reference Safety Information for the trial.
8. Preparing standard tables and other relevant information for the DSUR in collaboration with the CI and ensuring timely submission to the REC.

Trial Steering Committee (TSC):

In accordance with the Trial Terms of Reference for the TSC, periodically reviewing safety data.

9.5 Notification of deaths

The procedure for notification of death which does not constitute a SAR or SUSAR will be notification to sponsor by the chief investigator of only deaths that are assessed to be caused by the treatment will be reported to the sponsor. This report will be immediate.

9.6 Pregnancy Reporting Participants will be asked to report any pregnancy occurring within 28 days of trial enrolment. GPs will be asked for their assistance in relaying information regarding any pregnancies to the trial team. Any such pregnancies must be reported to the Chief Investigator and the Sponsor using the relevant Pregnancy Reporting Form. Pregnancy is not considered an AE unless a negative or consequential outcome is recorded for the mother or child/foetus. If the outcome meets the serious criteria, this would be considered an SAE.

9.7 Overdose

Participants will be advised in the PIS to contact the research team on for advice if they believe they have taken too much Sambucol/Placebo or an overdose. Participants will also be asked about their compliance with the recommended dosage during telephone consultations with the Research Staff. Emergency contact for 24hr

Overdose definition: More than 50 % excess dosage (> 90ml) in any 24 hour period. Identified during participant consultations. In the event of a confirmed overdose the participant will be withdrawn from the trial.

Any overdose event will be recorded as a protocol deviation and reported to the Sponsor.

9.8 Reporting urgent safety measures

If any urgent safety measures are taken the CI/Sponsor shall immediately and in any event no later than 3 days from the date the measures are taken, give written notice to the REC of the measures taken and the circumstances giving rise to those measures.

9.9 The type and duration of the follow-up of participants after adverse reactions.

Adverse reactions are extremely unlikely, however, after clinical assessment by the Investigator follow up will be advised accordingly as either no follow-up required, follow-up via patient's GP or via a Hospital appointment.

Any SUSAR will be reported to the Sponsor irrespective of how long after treatment administration the reaction has occurred until resolved.

9.10 Development safety update reports (DSURs)

The CI will provide (in addition to the expedited reporting above) DSURs once a year throughout the clinical trial, or as necessary, to the Research Ethics Committee and the sponsor.

The report will be submitted within 60 days of the Developmental International Birth Date (DIBD) of the trial each year until the trial is declared ended.

10 STATISTICS AND DATA ANALYSIS

10.1 Sample size calculation

The sample size was based on detecting a difference in the primary outcome, VAS symptoms score at 10 days, between groups. The standard deviation of the outcome is estimated to be 20 units, and a difference between groups of 10 units is regarded as being of clinical importance. With a 5%

BERRY Protocol v 6.2 22.07.2021 IRAS 282732

significance level and 90% power, it is calculated that 86 patients per group, 172 in total, are required. To allow for a 15% dropout, it is proposed that 204 patients are recruited into the study.

10.2 Planned recruitment rate

204 participants over 24 months

10.3 Statistical analysis plan

A full Statistical Analysis Plan (SAP) will be developed and agreed in advance of any data analysis.

10.3.1 Summary of baseline data and flow of patients

Summary statistics of all patient demographics and baseline data will be produced for each of the two study groups separately. Categorical variables will be summarised by the number and percentage of patients in each category. Continuous variables will be summarised by the mean and standard deviation if found to follow a Normal distribution, and the median and inter-quartile range otherwise.

The flow of patients through the trial will be illustrated by a Consort diagram.

10.3.2 Primary outcome analysis

The primary outcome, VAS symptoms score at 10 days, will be analysed using Analysis of Covariance (ANCOVA). The scores at 10 days will be used as the outcome variable, with the symptom scores at baseline included as a covariate.

The primary analysis will be performed on an Intention to Treat (ITT) basis. Participants will be analysed in the arm to which they were randomised, irrespective of whether they received their allocated treatment.

If the population varies for the ITT analysis, a per protocol analysis will be performed, as a sensitivity analysis.

10.3.3 Secondary outcome analysis

Secondary outcomes with a baseline measurement at baseline will be analysed using equivalent methods to the primary outcome. Secondary endpoints measured on a categorical scale will be compared between groups using the Chi-square test.

10.4 Subgroup analyses

None planned.

10.5 Adjusted analysis

No adjustments for baseline or demographic factors are planned

